# Project title Ketone Monitoring in T1D: Effect of SGLT2i during Usual Care and with Insulin Deficiency

#### **Project description**

# Rationale

Type 1 diabetes (T1D) continues to increase in incidence and in prevalence due to improved acute and chronic disease management. Despite developments over the past 20 years in short and long-acting insulins, in insulin administration through pen devices and insulin pumps, and more recently the addition of continuous glucose monitoring systems, glucose control has not improved substantially in persons with T1D. Consequently, the battle to reduce the incidence of long term complications such as diabetic nephropathy in persons with T1D has not been won. The risk of microvascular complications, particularly kidney disease, is strongly associated with the risk of cardiovascular disease in T1D. Both need improved prevention and treatment strategies.

Sodium-glucose cotransport2 inhibitors (SGLT2i) have been irrefutably proven to reduce progression of chronic kidney disease (CKD), hospitalizations for heart failure and death due to cardiovascular causes in persons with type 2 diabetes. Cardiovascular and kidney outcome trials have, in some cases, included persons without diabetes, and have shown equivalent benefits in these persons who are at high risk of serious health consequences from exacerbation of heart failure or from progression of CKD. While the results of the cardiovascular or renal outcome clinical trials have varied depending on the drug studied, the population included and the specified outcomes of interest, the results show such significant benefits that SGLT2i are now recommended by major guidelines for the management of persons with (and in some cases without) type 2 diabetes and either heart failure or CKD. However, there is a group of individuals at high risk of adverse cardiovascular and kidney outcomes for whom SGLT2i are not indicated or approved, and those persons have T1D.

Clinical trials of each of the SGLT2i have been conducted in T1D for purposes of gaining regulatory approval for use in this population for glucose lowering and amelioration of weight gain and in some cases reduction of hypoglycemia. The pivotal trials for glucose lowering are typically 24 – 26 weeks in length, with safety studies lasting 1 – 2 years. The trials have been conducted in adults with T1D, commonly with HbA1c levels greater than 7 – 7.5%. Most of the clinical programs in T1D have included two trials, so for each of the four SGLT2i (canagliflozin, empagliflozin, dapagliflozin and sotagliflozin), hundreds to more than a thousand persons with T1D have been included with more than half taking the active SGLT2i. With one exception of low dose empagliflozin (2.5 mg, a dose not otherwise available), there has been a consistent signal of increased occurrence of ketosis-related adverse events, including diabetic ketoacidosis (DKA). In general, the incidence of DKA in the SGLT2i groups is 2 – 3X the incidence in the placebo groups. This increase in DKA occurred despite ketone action plans that included provision of ketone meters and clear directives when patients developed symptoms of hyperketonemia or when ketones were elevated, strategies currently proposed by national groups to mitigate DKA. Since DKA can be a life-threatening event for persons with T1D, this increased risk is considered by regulatory agencies and most clinicians to be unacceptable, and thus persons with T1D are not able to benefit from the reduction in cardiovascular and kidney outcomes afforded by these agents.

Ketone generation, whether by fasting, insulin deficiency or other causes is the end result of complex metabolic pathways, and involves intermediates that have eluded clinical measurement, such as blood acetoacetate (AcAc) and acetone. Acetone is highly volatile and is excreted primarily through the lung, as shown below. The rapid breathing that occurs in T1D persons in DKA is an attempt to excrete acetone and reduce the level of circulating ketones. Acetone diffusion and excretion can be measured in exhaled air, ideally from alveolar spaces at the end of exhalation. Prior work has shown that there is a linear relationship between breath acetone (BrACE) and plasma acetone and between BrACE and beta hydroxybutyrate (BOHB) such that BrACE could be used in risk prediction model for diabetic ketoacidosis. A study that compared BrAce with blood BOHB in non-diabetic persons showed a relatively weak correlation, R=0.57, however the ROC analysis confirmed that BrAce can identify levels of ketosis that would be actionable to a person with T1D. BrACE is susceptible to interferences from foods, alcohol and environmental volatile organic compounds (VOC) such as hand sanitiizers, cleansers and nail polish remover, which needs consideration during home use.

There is still quite a lot to learn about the relationship between BrAce and BOHB levels, particularly in persons with T1D, who are at risk of ketosis and DKA. Is there a correlation between BrAce and BOHB in persons with fluctuating glucose and insulin levels, characteristic of T1D? Can measuring BrAce identify actionable levels of ketones with or without a strong correlation with BOHB? Do elevated ketones always occur in the setting of elevated blood glucose, or is there a risk of ketogenesis with low glucose such as when fasting? Monitoring of "ketone status" which is to say, identifying ketone levels that rise to actionable levels prior to the development of classic symptoms of ketosis, is now considered urgent.

Herring et al. propose that the increase in BOHB with the SGLT2i dapagliflozin is due to multiple factors, including increased lipolysis, reduced renal excretion, reduced uptake of BOHB by peripheral tissues and a metabolic switch to ketogenesis in the liver. Ferrannini et al found that in persons with type 2 diabetes (T2D), the increase in BOHB secondary to SGLT2i was due to overproduction of ketones. Diabetic ketoacidosis (DKA) with blood glucose that is lower than expected, known as euglycemic DKA, is now a recognized risk in persons with T2D who take SGLT2i. A similar phenomenon can occur in T1D.

We propose a study that includes both real world testing at home, and testing during insulin deficiency that is patterned after the studies by Patel et al and Herring et al. The study purpose, which is to

test whether measurement of BrAce, currently used to support persons on a ketogenic diet, can be repurposed for ketone tracking in persons with T1D. The choice of the Biosense® (Readout) breath ketone analyzer (BKA) was predicated on its designation as a Class 1 device by FDA. In the prior clinical trial in non-diabetic persons, both BrAce and blood BOHB were found to vary widely throughout the day. Multiple factors are known to create variability in ketone production and excretion in breath, including fasting, restriction in carbohydrate intake and exercise. Other factors at play may be cross contamination with other VOC such as alcohol, hand sanitizer, etc. The Biosense® BKA to be used in this study will have a filter to reduce the effects of competing substances during the on-site visits with insulin deficiency to mitigate this problem under controlled circumstances.

This proposed study of 4 distinct segments that include routine testing of ketones during usual care, during insulin deficiency, and while taking a SGLT2i in addition to usual care, then with insulin deficiency **after the SGLT2i has reached steady state** and ingested that morning. We will study 20 adults with T1D who are using Dexcom G6 continuous glucose monitor (CGM), plus any form of insulin delivery. Study participants will be randomized to Group A or Group B as shown below in Figure 1. Simultaneous ketone monitoring using a the Biosense® BKA and capillary blood BOHB measurement will be done 2-3X daily for 2 weeks during each of the outpatient segments. This will generate >800 data points comparing breath acetone, measured in units called ACEs, versus capillary blood BOHB measurements for each 2 week period. On days of insulin withdrawal, which will take place on the Washington University Intensive Research Unit (IRU), frequent monitoring with capillary blood measurements of BOHB (Precision Xtra®, Abbott) will be compared with breath BrAce measurements (Biosense®, Readout) and laboratory measurements of BOHB and acetoacetate. Electrolytes and glucose will also be measured. The schematic is shown below:

Figure 1. Study plan and study groups.

The goals of the study are to better understand ketone fluctuations in persons with T1D during usual care and when taking a SGLT2i in addition to usual care through frequent ketone monitoring. Additional information about usability of the breath ketone analyzer will be tested with simple questions using a Likert scale and a structured interview at the end of the study. The question is not whether the ketone measurements correlate perfectly with the gold standard BOHB measurements, but whether breath ketone measurements by the Biosense BKA are adequate for patients to understand their "ketone status" and identify states of rising ketones early enough for mitigation strategies to work. The potential advantages of using a breath analyzer are that it is non-invasive; it is easy to use repeatedly without additional cost or pain from fingersticks, and it may be sufficiently informative to employ a ketone action plan before ketones rise to hazardous levels.

The long term goals of this study extend beyond the completion of the study to the development of DKA mitigation strategies that are manageable and accepted by patients. A ketone mitigation strategy must

identify excess ketones before symptoms of hyperketonemia or DKA occur. A successful DKA mitigation strategy could be deployed in patients with recurrences of DKA and in those for whom a SGLT2i is indicated for reduction of cardiovascular or renal adverse outcomes. The mitigation strategies would need to be tested in a multi-center clinical trial conducted over longer periods of time in populations or with interventions of interest. This study offers a novel approach to ketone detection that has not been previously tested in persons with T1D.

# **Objective(s)**

The objectives of this study are several, and the following hypotheses will be tested:

- 1. Ketone generation in persons with T1D can be identified by measuring capillary betahydroxybutyrate or breath acetone using a breath ketone analyzer during insulin deficiency, and the values will show a significant correlation.
- 2. Breath ketone measurements tested during usual care will correlate with capillary blood measurement of beta-hydroxybutyrate.
- 3. SGLT2i use will increase blood and breath ketones in persons with T1D during insulin deficiency, and simultaneous measurements of blood beta-hydroxybutyrate and breath acetone will show a significant correlation.
- 4. Breath ketone measurements tested during 2-weeks of SGLT2i therapy will correlate with capillary blood measurements of beta-hydroxybutyrate.
- Patients will be able to identify episodes of ketogenesis during usual care and usual care plus SGLT2i therapy prospectively, before symptoms of ketosis occur, with the breath ketone analyzer.
- 6. Use of the breath ketone analyzer will be accepted by persons with T1D for routine and symptomatic monitoring of ketone levels such that mitigation strategies can be employed before elevations in ketones become severe.

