- Segment 1 will consist of 2 weeks of usual care with participants measuring fasting and random breath ketones paired with capillary BOHB (Group A) or usual care plus dapagliflozin with participants measuring fasting and random breath ketones paired with Capillary BOHB (Group B). Participants will be instructed to do paired ketone testing anytime their glucose is >250 mg/dL, or if they develop symptoms of feeling unwell for any reason.
- 3. Visit 2 will be a single day of on-site close monitoring during insulin withdrawal. Morning insulin doses will be withheld, and the participants will have hourly checks of glucose, capillary BOHB, breath ketones, blood BOHB and acetoacetate. CBC will be done at baseline, and BMP to check electrolytes will be done at baseline and every 2 hours until the study end. Instructions for Segment 2 will be provided and recommendations for change in insulin regimen or insulin doses will be made at this visit.
- 4. Segment 2 will consist of 2 weeks of usual care (Group B) or usual care plus therapy with dapagliflozin SGLT2i (Group A). Participants will be instructed to do paired ketone testing fasting and randomly during the day, and if their CGM glucose exceeds 250 mg/dl or if they feel unwell.
- 5. Visit 3 will be a single day of on-site close monitoring during insulin withdrawal (Group B), but after taking an SGLT2i tablet (Group A). Morning insulin doses will be withheld, and the participants will have hourly checks of glucose, capillary BOHB, breath ketones, blood BOHB and acetoacetate. CBC will be done at baseline, and BMP to check electrolytes will be done at baseline and every 2 hours until the study end.

The study design and schematics are depicted below:

	Phone								Visit 3 /FOS
GROUP A	or clinic visit	Visit 1	Gap d	Usual Care + Ketone Monitoring	Visit 2 IRU Insulin Withdrawal	Gap e	Optional Visit	Usual Care + SGLT2i + Ketone Monitoring	IRU Insulin Withdrawal
		On-site		HOME- Segment 1 14 +/-2 days	On-site		Phone or on-site	HOME - Segment 2 14 consecutive	On-site
Phone screening	х								
Informed Consent discussion	Х	Х							
Informed Consent	X	X							
Demographics, medical, medication and		v							
Vital signs, height, weight		×							
Inclusion/exclusion review	x	x							
Physician H&P	~	X							
Near Vision Accuity Screening		x							
CGM check for connectivity to clinic		X							
Dispense capillary ketone meter and									
supplies, breath ketone analyzer		X							

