After the investigator or sub-investigator determines that the participant meets all of the inclusion and none of the exclusion criteria, the study team will proceed with interrogation of the participant's CGM to ensure appropriate connectivity with the study team. Participants will be asked to demonstrate competency in making changes to insulin pump settings. The study team members will train the participant in the use of the Precision Xtra ketone meter and the Biosense BKA. Participants will be instructed to wait 60 minutes after eating, smoking/vaping, drinking sodas or flavored waters or consuming items such as toothpaste, mouthwash, cough drops, breath mints, chewing gum, lip balm and artificial sweeteners before doing a BrACE measurement. If using alcohol, participants should wait 4 hours before testing with the BKA. Participants will be instructed in avoidance of environmental contaminants also. Participants will be able to test capillary BOHB even when conditions are not optimal for BrACE.

The participant will upload the Biosense app onto his or her smart phone and test a test run will be conducted. A diary will be provided for entry of BOHB ketone measurements and BrAce with space for comments in case of known interference with BrAce or other problems with measurements. A written ketone action plan will be provided to all participants in the study. Participants will be informed that they may stop participating in the study at any time without loss of usual care of their diabetes.

A ketone action plan will be provided to each participant that will include the following elements: ingestion of carbohydrates, fluid intake and insulin administration with doses of insulin adjusted according to individual requirements. Participants will be asked to employ the ketone action plan if BOHB reading is >1.5 mmol/L. BrACE levels of >15 in the absence of corresponding BOHB level >1.5 mmol will be considered due to contamination and the participant will be asked to repeat the levels in 1 - 2 hours.

Patients will be randomized by card draw in lots of 4 to Group A or Group B

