**USUAL CARE** (Group A will do this first, Group B will do this segment after the SGLT2i) The participant will manage his or her diabetes in the usual way, with no effort to modulate glucose levels for the study. Participants will check breath ketones with the Biosense BKA and capillary BOHB with the Precision Xtra ketone meter when fasting and at one or two other times during the day, plus any optional measurements. See instructions above for avoidance of biologic or environmental contaminants. There is no mandated contact with the participant, but participants can contact the study team at any time for questions, to report device issues or discuss glucose or ketone levels.

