#### Assessment of Efficacy

The main efficacy parameter will be the correlation between BrAce levels and capillary blood BOHB levels during segments 1 and 2, usual care and usual care + SGLT2i of the study using linear regression. Efficacy will be established with  $R^2 > 0.6$ . Separate linear regressions will determine the correlation of BrAce levels with capillary blood BOHB, of BrAce levels and laboratory BOHB, and of BrAce levels and AcAc. Efficacy of BrAce for correctly indicating actionable ketosis will be established with  $R^2 > 0.6$ . Additionally, a receiver operating characteristic (ROC) analysis will be performed to clarify the diagnostic ability of BrAce compared to capillary blood BOHB to correctly or incorrectly identify ketone levels that would be considered actionable for a person with T1D, or >1.5 mmol/L.

Qualitative analysis will be undertaken based on a simple Likert scale questionnaire with the following questions rated from 1 to 5:

- Did testing breath ketones help you to understand your "ketone status"?
- Were you able to identify episodes of mild ketosis with the Biosense breath ketone analyzer?
- Are you likely to continue to use the Biosense breath ketone analyzer for this purpose?

The main efficacy parameter will be assessed with an interim analysis after completion of 12 subjects in the trial, with results reported to the DSMB and to the funding partner, JDRF. Adverse events will be manually tabulated and reported.

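### Objective 5: the plan can show whether the breath reading discriminates raised BOHB, but not whether patients recognise ketosis from breath before symptoms

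*Combined protocol and SAP*

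**What the plan says.** All references are to the combined protocol and SAP.

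- **Objective(s), fifth hypothesis.** Among the hypotheses to be tested: "Patients will be able to identify episodes of ketogenesis during usual care and usual care plus SGLT2i therapy prospectively, before symptoms of ketosis occur". The stated means is the breath analyzer.
- **Home testing.** The Rationale states: "Simultaneous ketone monitoring using a the Biosense® BKA and capillary blood BOHB measurement will be done 2-3X daily for 2 weeks". The Usual Care segment states: "Participants will check breath ketones with the Biosense BKA and capillary BOHB with the Precision Xtra ketone meter when fasting". One or two further daily tests follow in that segment; the SGLT2i segment asks for two. Research Design adds event-driven tests, also paired: "Participants will be instructed to do paired ketone testing anytime their glucose is >250 mg/dL, or if they develop symptoms of feeling unwell". Data Management and Analysis requires only that the two readings fall within one hour of each other. No order or masking is given.
- **Action.** Visit 1 states: "Participants will be asked to employ the ketone action plan if BOHB reading is >1.5 mmol/L". It also states: "BrACE levels of >15 in the absence of corresponding BOHB level >1.5 mmol will be considered due to contamination", after which the participant repeats the test. The on-site visit text and Assessment of Safety have similar rules.
- **Recording.** Visit 1 states: "A diary will be provided for entry of BOHB ketone measurements and BrAce with space for comments in case of known interference with BrAce". The comment space also covers further measurement problems.
- **Patient-level outcome.** Assessment of Efficacy lists three items scored 1 to 5, among them: "Were you able to identify episodes of mild ketosis with the Biosense breath ketone analyzer". The visit schedules show the survey twice in each group, and the Rationale mentions a structured interview at study end.
- **Analysis.** Assessment of Efficacy and Statistics plan correlations and a ROC curve of BrACE against capillary BOHB above 1.5 mmol/L. Likert values are reported as mean and SD.

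**The concern.** Objective 5 has three parts: the patient does the identifying, the breath analyzer is the source, and it happens before symptoms. Each part needs something recorded at the time of the test, and the plan describes no such record. A participant who later reports having spotted mild ketosis with the analyzer may have learned of it from the finger-stick taken at the same session. The rule that a high breath value without raised BOHB counts as contamination also teaches participants to let the blood result decide.

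At stake is the claim made at the end. A good ROC curve and a high Likert score could be read together as proof that patients can track ketosis by breath alone. Only the first would be evidence about breath, and it concerns the device. The Likert item on understanding one's ketone status has the same weakness, and so does support for objective 6, which concerns monitoring early enough to act.

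**Working it through.** **1. Data volume.** Inputs: 20 participants (Rationale), 14 days per segment, 2 to 3 tests a day.

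- Per segment: 20 × 14 × 2 = 560; 20 × 14 × 3 = 840. The stated figure of more than 800 per segment needs three tests a day with almost no losses.
- Both segments: 20 × 28 × 2 = 1,120; 20 × 28 × 3 = 1,680. At 2.5 a day, 20 × 28 × 2.5 = 1,400, which reproduces the approximate total in Sample Size.

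The total is therefore sound for correlation and ROC work. No sample size, episode definition or success criterion is given for objective 5.

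**2. Each part of objective 5 set against the plan.**

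| Part | What is needed | What is described |
|---|---|---|
| Breath signals raised ketones | Paired values | Yes: ROC of BrACE against BOHB |
| The patient recognises it from breath | Judgement logged before BOHB is seen | No test order; no diary entry for a judgement |
| Before symptoms | Symptom status at each reading | Not described for the diary; some information from triggered tests and event follow-up |
| Analysis | Calls against BOHB, by symptom status | None in Statistics |

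The planned ROC also pools home pairs with the supervised insulin-withdrawal days, whereas objective 5 concerns the home segments.

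**3. Why a judgement made with BOHB known cannot be credited to breath.** This is an illustration; every value is assumed. Suppose a patient relies on BOHB in a fraction *f* of episodes and on breath, with sensitivity *s*, in the rest. BOHB defines the episode, so it is always right by construction:

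apparent sensitivity = *f* + (1 − *f*) × *s*

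| *f* | *s* = 0.2 | *s* = 0.5 | *s* = 0.8 |
|---|---|---|---|
| 0 | 0.20 | 0.50 | 0.80 |
| 0.5 | 0.60 | 0.75 | 0.90 |
| 0.9 | 0.92 | 0.95 | 0.98 |
| 1 | 1.00 | 1.00 | 1.00 |

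At *f* = 0.9, poor and good breath recognition differ by only 0.98 − 0.92 = 0.06. Because *f* is unknown, *s* cannot be recovered, and more pairs do not change that.

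**4. Precision a recorded judgement would give.** The documents give no expected number of home episodes. If 80% were called correctly, the Wilson 95% intervals, before allowing for clustering within participant, would be:

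| Episodes | Called | Interval |
|---|---|---|
| 5 | 4 | 0.38–0.96 |
| 10 | 8 | 0.49–0.94 |
| 20 | 16 | 0.58–0.92 |
| 40 | 32 | 0.65–0.90 |

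Assessment of Safety cites BOHB of 1.2 mmol/L (untreated) and 1.5 mmol/L (with canagliflozin) after six hours of insulin withdrawal in a similar study. Home readings above 1.5 mmol/L may therefore be few.

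**The case against.** The strongest reply is that objective 5 is really about the device. Sample Size says the main aim is whether the analyzer gives enough information for a patient to consider acting, and calls the ROC analysis crucial. Seeing a finger-stick does not change the number the analyzer shows. The Rationale's statement of the study question likewise concerns whether the measurements are adequate. This stands for the device-level question, which remains answerable. It does not reach objective 5 as worded, which names patients, prospective identification and symptoms.

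A reader might infer several stronger things that the documents do not support:

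- *That every breath value is read with the blood answer in view.* Order is unstated and pairs may be up to an hour apart, so some breath values may well be read first. The problem is that nobody will know which.
- *That a single Likert item is the only patient-level evidence.* The survey is scheduled twice per group and there is a closing interview. Both are still retrospective and informed by BOHB.
- *That no symptom information will exist.* Feeling unwell triggers a paired test, BOHB above 1.5 mmol/L leads to contact with study staff, and adverse events are reviewed. The diary form itself is not reproduced. However, no symptom status linked to each breath reading is described.
- *That breath plays no part in action.* A high breath value without raised BOHB prompts a repeat test. The ketone action plan itself is triggered by BOHB.

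It is also fair that objective 5 is neither primary nor powered.

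**Conclusion.** The point holds for the patient-level, pre-symptom part of objective 5. It would be wrong to say that objective 5 cannot be answered at all: discrimination of BOHB by the device reading is covered by the ROC analysis, most relevantly if the home pairs are also shown separately. For patient recognition, the plan describes no contemporaneous judgement at any of the 1,120 to 1,680 scheduled home pairs and no analysis that would use one. What remains is retrospective opinion from at most 20 people who knew their BOHB.

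The conclusion rests on the diary being as described in Visit 1 and on no test order being set elsewhere, for example in training material. If either assumption is wrong, the gap narrows accordingly. The primary correlation outcome is unaffected. The change is worth making before enrolment because these judgements cannot be reconstructed afterwards.

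**What to change.** **At scheduled home pairs only:** take the breath reading first. Before the finger-stick, tick in the diary *ketones raised: yes / no / unsure* and *symptoms now: yes / no*. Then measure BOHB. Leave symptom- or glucose-triggered tests, BOHB testing when breath conditions are unsuitable, and all action rules exactly as they are.

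**Add to Statistics**, by segment and for the home segments only:

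- the proportion of symptom-free readings with BOHB above 1.5 mmol/L that were called *yes* on breath;
- the same for a prespecified lower level, such as the 0.5 or 1.0 mM thresholds in Sample Size;
- the false-call rate at each level.

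Report these descriptively, with intervals that allow for clustering within participant, and keep the Likert items as secondary.

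**Cost.** Two ticks at each of 56 to 84 tests per participant (28 × 2 to 28 × 3), one line of training and a short tabulation. Order-keeping relies on unmasked participants, earlier BOHB results may still inform later calls, and estimates may be imprecise if episodes are few.

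**If this is not adopted,** reword objective 5 as device discrimination, and do not credit the Likert answers to the breath analyzer alone.

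Separately, the BOHB level below which a breath value above 15 is put down to contamination is 1.5 mmol/L in Visit 1 and the on-site visit text but 1.0 mmol/L in Assessment of Safety. These passages must be reconciled.
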